8.11.3 Fatty Acids in Plasma and Red Blood Cell Membranes

Fatty acids to be assessed include linoleic acid, α -linolenic acid, Mead acid, eicosapentaenoic acid, arachidonic acid, docosahexaenoic acid. The fatty acids and absolute and relative change from baseline will be summarized descriptively by underlying disease group and treatment group.

The incidence of essential fatty acid deficiency and shift from baseline will be summarized with descriptive statistics by treatment group. Essential fatty acid deficiency is based on the ratio of Mead acid and Arachidonic acid (also called the triene/tetraene ratio or Holman index; Holman, 1960). A ratio of > 0.2 will be considered abnormal (=essential fatty acid deficiency; Holman et al., 1979). The Holman index (= triene/tetraene ratio) will be calculated by statistical programming.

8.12 Analysis of Secondary Safety Variables

The analysis of the secondary safety endpoints will be performed using the safety analysis set. All analysis of the secondary safety endpoints will be descriptive, no statistical hypothesis testing will be performed. Unless otherwise stated, safety endpoints will be presented using data from the initial and extension phase combined. For all safety endpoints data from both stages of the group-sequential design will be combined.

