- **Early discontinuation:**

Should conjugated bilirubin exceed 2 mg/dL (> 2 mg/dL), a confirmatory analysis must be performed after 7 days. The patient's dose will remain at 1 g/kg/day until analysis of the confirmatory blood sample. If the confirmatory analysis reveals that conjugated bilirubin increased further by at least 1 mg/dL, then the patient has to be removed from the study immediately and may be treated with an alternative lipid emulsion at the investigator's discretion. If not, the patient continues to receive study medication.

- **Weaning of lipids and PN:**

As soon as the patient receives 80 mL/kg/day oral/enteral feeding and achieved tolerance (i.e. at least 3 days) the dose of study drug must be reduced to 1 g/kg/d.

As soon as patient receives 100 mL/kg/day oral/enteral feeding and achieved tolerance (i.e. at least 3 days) study drug must be stopped completely.

Duration of Treatment:

The expected administration of lipid emulsions for each study patient should be 28 days. If PN is still indicated after 28 days, patients may receive the study drug for up to 84 days.

Patients:

Hospitalized neonates and infants, expected to require PN for 28 days

Clinical Study Protocol SMOF-018-CP3

Smoflipid 20% lipid injectable emulsion

Inclusion Criteria:

1. Neonates and infants, expected to require PN for 28 days
2. Postmenstrual age \geq 24 weeks
3. Birth weight \geq 750g
4. Gastrochisis, duodenal, jejunal or ileal atresia, volvulus, spontaneous intestinal perforation or necrotizing enterocolitis (Bell's stage 2B or higher)
5. At least 80% of nutritional needs at Baseline are met with PN
6. Signed and dated informed consent obtained from at least one parent or legal guardian

Exclusion Criteria:

1. Conjugated bilirubin > 0.6 mg/dL
2. Any known pre-, intra- or posthepatic complication that will increase conjugated bilirubin levels > 0.6 mg/dL during study participation
3. Suspected liver disease or liver damage based on either AST, ALT, or GGT exceeding 2.5x upper limit of normal range
4. Active bloodstream infection demonstrated by positive blood culture at screening
5. Cystic fibrosis
6. Meconium ileus
7. Serum TGs > 250 mg/dL
8. Cyanotic congenital heart defect
9. Severe renal failure as evidenced by creatinine > 2.0 mg/dL
10. History of shock requiring vasopressors
11. Anasarca
12. Extracorporeal Membrane Oxygenation (ECMO)
13. Known inborn errors of metabolism
14. Known congenital viral infection

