10.4 Withdrawal of Patients from the Study

Patients withdrawn from study after randomization but before receiving any study drug will be counted as “early drop-outs”. These patients will be replaced and will not undergo additional assessments.

The patient’s parent or guardian may voluntarily withdraw the patient from participation in the study or prevent the administration of study medication at any time without needing to provide any reason.

If the Investigator has to withdraw a patient from the study, or if the patient’s parent(s) or legal guardian(s) refuses to have the patient continue with study participation, patient’s parents or legal representatives should be asked to allow that the assessments for the Final Visit the day after receiving the last dose of study medication are completed. The reason(s) for study withdrawal must be documented.

Patients who are withdrawn from the study due to AEs or SAEs will be treated and followed according to established medical practice to evaluate the course of the AE and ensure reversibility or stabilization (also see Section 13).

The following are justifiable reasons for the Investigator to withdraw a patient from the study:

- Intolerable AEs/SAEs
- Deteriorating liver function (see below)
- Unacceptable risk/benefit ratio
- Major protocol deviation(s)

Major protocol deviations are those that may significantly impact the completeness, accuracy, and/or reliability of the study data or may affect the patient’s rights, safety, or well-being. In case of any potential major deviation, the Investigator has to notify the CRA immediately.

Fresenius Kabi reserves the right to discontinue the entire study for internal reasons at any time (see also Section 16.3).

Withdrawal Due to Deteriorating Liver Function

If conjugated bilirubin levels exceed 2 mg/dL, a confirmatory sample must be assessed after 7 days. If conjugated bilirubin levels have increased by at least 1 mg/dL, the Investigator must withdraw the patient from the study so the patient can receive an alternative lipid emulsion according to standard of care. If conjugated bilirubin levels increased less than 1 mg/dL, the patient will remain in the study and continue to receive study medication. Weekly conjugated bilirubin analyses must be performed until the patient’s conjugated bilirubin level is again \leq 1.5 mg/dL.

Clinical Study Protocol SMOF-018-CP3
Smoflipid 20% lipid injectable emulsion

11 Study Drugs and Medication

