12.2.7 Follow-Up Visit

The Follow-Up Visit will be performed 7 days after the End-of-Treatment Visit to ensure the safety of the patient after study participation.

The following procedures have to be performed:

- Recording of adverse events
- Recording of concomitant medication
- Recording of physical examination and body measurements
 - physical examination
 - body weight
 - body length measured by a length board
 - head circumference
- Recording of vital signs
 - blood pressure
 - heart rate
 - body temperature
- Recording of Length of Stay in the hospital

Clinical Study Protocol SMOF-018-CP3 Smoflipid 20% lipid injectable emulsion

- Recording of AEs
- Recording of concomitant medication

The Length of Stay in the hospital will be calculated using the worksheet provided in Annex 4 to this protocol.

All unresolved AE and SAEs will be followed by the Investigator until the events are resolved, the patient is lost to follow-up, or the adverse event is otherwise explained.

All patients that had conjugated bilirubin levels >1.5 mg/dL at the Follow up visit will have the conjugated bilirubin level assessed at the Follow-Up Visit, and then it should be assessed weekly until conjugated bilirubin is again ≤ 1.5 mg/dL.

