8.12.4 Adverse Events, Serious Adverse Events, Deaths

All reported terms (investigator descriptions) for AEs will be coded using the version of the Medical Dictionary for Regulatory Activities (MedDRA) at database closure and will be summarized descriptively.

A treatment-emergent adverse event (TEAE) is an event that emerges during treatment, having been absent pre-treatment, or worsens relative to the pre-treatment state.

For all AE summaries, events will be counted only once for a given patient by primary system organ class and preferred term. When an AE occurs more than once for a patient, the maximum severity and causality will be used. Missing severity will not be imputed but counted as a separate category. AEs which are not rated as “not related” will be reported as related according to the study protocol and sponsor standards.

The following summaries will be presented with numbers and percentage of patients with the event and number of reported events for each system organ classification and preferred term by underlying disease group and treatment group:

- All AEs
- All TEAEs
- TEAEs leading to discontinuation from the study
- TEAEs by relation to study procedure
- TEAEs by relation to study drug (relationship was reported as “related” or “unrelated”).
- TEAEs by CTCAE severity
- TEAEs by relation to study drug and CTCAE severity
- TEAEs occurring with an incidence > 5 % within any treatment arm
- All serious TEAEs (see Section 13.1.2 of the protocol)
- Serious TEAEs by relation to study drug

Statistical Analysis Plan

FK Study Identifier: SMOF-018-CP3

- TEAEs with fatal outcome

In addition, the number and percentage of patients with the event of the following TEAEs of special interest (syndromes reported as AEs) will be presented by treatment group:

- all major neonatal morbidities
- bronchopulmonary dysplasia
- retinopathy of prematurity
- intraventricular hemorrhage
- periventricular leukomalacia
- necrotizing enterocolitis
- late-onset sepsis in premature and low birth weight neonates.

The following AEs will also be presented by treatment group for each subgroup of ethnicity and race category, respectively:

- All AEs
- All TEAEs
- TEAEs leading to discontinuation from the study
- TEAEs by relation to study procedure
- TEAEs by relation to study drug
- TEAEs by CTCAE severity
- All serious TEAEs (see Section 13.1.2 of the protocol)
- TEAEs with fatal outcome
- TEAEs of special interest, as defined above

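### Adverse events are shown only as crude percentages pooled over both phases, although observation runs from about 9 to about 92 days and may differ by arm in either direction

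*SAP*

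**What the plan says.** SAP 8.12 pools the phases by default: "Unless otherwise stated, safety endpoints will be presented using data from the initial and extension phase combined". SAP 8.12.4 states no exception for adverse events. Its main tables give "numbers and percentage of patients with the event and number of reported events for each system organ classification and preferred term", and "events will be counted only once for a given patient by primary system organ class and preferred term". Special-interest events (bronchopulmonary dysplasia, retinopathy, intraventricular hemorrhage, periventricular leukomalacia, necrotizing enterocolitis, late-onset sepsis) get number and percentage of patients. The table list in SAP 9 contains no adverse event table by patient-time, by phase or over a fixed window.

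The length of observation follows from the protocol:

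- Study Outline, Duration of Treatment: if parenteral nutrition (PN) is still indicated after 28 days, "patients may receive the study drug for up to 84 days".
- 12.2.7: "The Follow-Up Visit will be performed 7 days after the End-of-Treatment Visit". Section 13.3.5 ends the observation period at the last follow-up visit.
- 10.4: after a value above 2 mg/dL, if the 7-day sample shows a rise of at least 1 mg/dL, "the Investigator must withdraw the patient from the study so the patient can receive an alternative lipid emulsion". With a smaller rise the infant stays on study drug.
- 11.3: infants who tolerate sufficient enteral or oral feeds are weaned off study drug.

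Other safety endpoints are handled differently. SAP 8.12.2 divides bloodstream infections by days on study medication and shows them by phase. SAP 8.12.1 uses competing-risk methods for discharge and for time to bilirubin above 2 mg/dL. Those endpoints are not part of this point.

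**The concern.** A crude percentage compares arms fairly only if infants in both arms are watched for about the same time. Here the time varies about tenfold, and two of the events that end it, bilirubin-driven withdrawal and weaning, can respond to treatment. Time to full feeds is itself a between-arm endpoint (SAP 8.11.2). Randomization therefore does not make observation time equal.

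With no hypothesis tests planned, readers will judge overall safety from these side-by-side percentages. An arm that is watched longer shows more infants with events at the same daily rate. The table of events above 5% in any arm has the same dependence on follow-up length. The plan relates bloodstream infections to drug days, but not deaths, serious events or major neonatal morbidities.

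**Working it through.** The documents give no figure for this point, so there is none to reproduce.

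**Observation window**

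- Longest: last dose Day 84, End-of-Treatment Visit Day 85, follow-up 85 + 7 = Day 92 (Day 94 with the +1 windows of both visits).
- Shortest with a completed follow-up visit: one dose on Day 1, visit Day 2, follow-up 2 + 7 = Day 9. Death or loss to follow-up makes it shorter.
- Earliest mandatory bilirubin withdrawal: Day 8 sample, Day 15 confirmation, follow-up about Day 22-23.

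**Dependence of a crude percentage on time**

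Assume a constant hazard and a 28-day event risk of 30% (not in the documents). The daily rate is −ln(0.70)/28 = 0.0127, and risk over t days is 1 − exp(−0.0127 t):

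| Days observed | Crude risk |
|---|---|
| 9 | 11% |
| 23 | 25% |
| 36 | 37% |
| 92 | 69% |

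**Difference between arms when the true daily rate is equal**

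Inputs from the protocol:

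- median PN duration 28 days, with about 15% still on PN at 3 months (7.2);
- cholestasis 40% on Intralipid and 18% on Smoflipid (Table 1, average case);
- 84-day cap on study drug.

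Assumptions not in the documents:

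- Weibull PN duration: shape = ln[ln(1/0.15)/ln 2]/ln(90/28) = 0.862, scale = 28/(ln 2)^(1/0.862) = 42.8 days;
- observation = days on drug + 8;
- forced withdrawal equally likely on Day 15, 22, 29 or 36;
- 10% to 100% of cholestatic infants forced out;
- PN in cholestatic infants would otherwise last 1, 1.5 or 2 times as long as in others;
- 28-day event risk 10%, 30% or 50%.

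Selected results at 30% risk (S = Smoflipid, I = Intralipid):

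| PN multiple | Forced out | Mean days S / I | Infants with event S / I | S − I, points | Ratio I/S |
|---|---|---|---|---|---|
| 1 | 100% | 41.2 / 37.1 | 37.3% / 34.7% | +2.6 | 0.93 |
| 1 | 30% | 43.5 / 42.2 | 38.8% / 38.0% | +0.8 | 0.98 |
| 1.5 | 30% | 44.7 / 44.9 | 39.6% / 39.8% | −0.2 | 1.01 |
| 2 | 50% | 44.4 / 44.3 | 39.4% / 39.5% | −0.1 | 1.00 |
| 2 | 10% | 46.6 / 49.2 | 40.8% / 42.5% | −1.7 | 1.04 |

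Over all scenarios, mean observation on Intralipid is 0.90 to 1.06 times that on Smoflipid. The crude ratio I/S runs from 0.91 to 1.05, and the difference S − I from +2.8 to −1.9 points. The true rate ratio is 1 throughout, which a per-day rate would return here because the simulated hazards are equal.

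The simulation does not let weaning time differ by arm other than through cholestasis, so it does not bound the total effect.

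**The case against.** A reader might infer that the arm with more cholestasis must get less observation time, so that the tables are biased against Smoflipid under the trial's own hypothesis. The documents do not support this:

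- Only a further rise of at least 1 mg/dL forces withdrawal. Other cholestatic infants continue (protocol 10.4, 11.3).
- Bilirubin above 1.5 mg/dL is a listed condition for continuing after Day 29 (protocol 12.2.5).
- Infants who do well also leave early, through weaning.
- Forced exits at about Day 15-36 straddle the 28-day median PN duration.

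A reader might also assume a large gap, such as mean observation of 30 v 40 days at a daily rate of 0.02. That gives 1 − exp(−0.6) = 45.1% v 1 − exp(−0.8) = 55.1%, a ratio of 1.22. To produce a 10-day gap by forced withdrawal alone, with a 22-point difference in cholestasis, each cholestatic infant would have to lose 10/0.22 = 45 days even if all were withdrawn. Nothing in the documents suggests that.

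Two further objections have weight. First, the SAP already tabulates drug exposure by arm (8.6), reasons for discontinuation (8.1), bilirubin withdrawals by arm and phase (8.12.2) and the cumulative incidence of full feeds (8.11.2). A reader can therefore see whether exposure differs. Drug exposure is neither adverse event observation time nor time to first event, however, so event rates cannot be derived from those tables. Second, "All analysis of the secondary safety endpoints will be descriptive, no statistical hypothesis testing will be performed". This limits how serious the point is, but a descriptive percentage can still mislead.

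Finally, a per-day rate does not cure informative withdrawal. That is correct, and it limits what the fix can deliver.

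**Conclusion.** The point holds for adverse event tables only. They are crude, pooled over phases, and rest on observation times from about 9 to about 92 days that end for outcome-related reasons. Observation may differ by arm in either direction, and the documents do not determine which.

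The likely distortion is modest: a crude ratio (Intralipid/Smoflipid) of about 0.91 to 1.05, or up to about 3 percentage points. This rests on the 40% v 18% case and on the assumed withdrawal shares, PN durations, event risks and constant hazard. For scale, SAP 8.8 reports 152 randomized infants at the interim. With an assumed even split of 76 per arm, 2.8 points is 0.028 × 76 = about 2 infants.

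The change is worth making because it is cheap and uses data already collected. It is not a reason to discard the crude tables or to claim bias against either product.

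**What to change.** Keep the crude tables. For treatment-emergent, serious treatment-emergent, fatal and special-interest events, add:

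1. Infants with a first event per 100 infant-days at risk, by arm, with a descriptive rate ratio and 95% CI. Time at risk runs to the first event, otherwise to the end of the window. First state whether the follow-up week counts as treatment-emergent, since the definition in SAP 8.12.4 leaves this open. Use that same window for events and for time at risk.
2. The same tables, with rates, restricted to the initial phase, Days 1-28 as in SAP 8.6. Percentages alone would not suffice, because infants can leave before Day 28.
3. Adverse event observation time by arm, with the reason it ended. For infants followed after treatment only for bilirubin, protocol 12.2.5 (no further evaluations) and 13.3.5 (observation to the last follow-up visit) should be reconciled so that the end date is unambiguous.

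The cost is a few extra columns and one repeat of the main tables. The rate assumes a roughly constant hazard, which the Days 1-28 tables make less critical. It does not remove informative withdrawal, and the report should state this as a limitation.

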8.12.1 Time to Event Variables

All time to event variables will be summarized with descriptive statistics using competing risk analysis. A detailed data listing for each time to event variable will be included.

8.12.1.1 Time to discharge from hospital

Length of stay in hospital (time from randomization to discharge) will be calculated using the Worksheet of the Vermont Oxford Network (see Annex 6 to the protocol). Death during hospitalization will be considered a competing risk. Patients alive who are not reported to be discharged during the study will be censored at the last follow-up date.

The cumulative incidence function for time to discharge from hospital will be estimated using the Aalen estimator (Aalen, 1978). The cause-specific hazard will be estimated using the subdistribution hazard model according to Fine and Gray with factors treatment, underlying disease group (No NEC / NEC) and the interaction term (Fine & Gray, 1999).

Statistical Analysis Plan

FK Study Identifier: SMOF-018-CP3

The number of patients discharged from hospital, the number of patients who died, the number of patients censored, the median time to discharge from hospital determined from the cumulative incidence function and the hazard ratio and its 95% confidence interval estimated determined from the Fine and Gray-model will be presented in a summary table.

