5.2 Rationale and Purpose of the Study

Fresenius Kabi, the manufacturer of Smoflipid, has applied for approval of Smoflipid in the United States (US). In order to meet the request of the Food and Drug Administration (FDA), a post-marketing study will be performed in hospitalized neonates and infants to show safety superiority of Smoflipid compared with Intralipid, a currently approved lipid emulsion in the US.

The present protocol describes a randomized, controlled, double-blind study in which either Smoflipid or Intralipid will be administered as part of a well-defined PN regimen to hospitalized preterm and term neonates and infants requiring at least 28 days of PN. The purpose of this study is to demonstrate the superiority in safety of Smoflipid (investigational drug) compared with Intralipid (reference drug) by evaluating the effect of these products on conjugated serum bilirubin levels. In addition, the study will explore if Smoflipid safely provides sufficient energy and essential fatty acids (EFAs) to ensure appropriate growth and development in these pediatric patients.

Sterols (including phytosterols) and α -tocopherol in the blood of the study patients will be evaluated to assess whether a correlation exists between the sterol and/or α -tocopherol levels and the incidence of cholestasis ([Burrin, et al. 2014](#), [Clayton, et al. 1998](#), [Ng, et al. 2015](#)), to address specific concerns communicated by the FDA given published experimental data ([Carter, et al. 2007](#), [El Kasmi, et al. 2013](#)).

Per the request of the FDA, length of stay in hospital, the number of independent bloodstream infections and mortality (as part of serious adverse event [SAE] analyses) will be evaluated as well.

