During treatment the following data must be documented daily: study drug administered, dextrose administered, amino acids administered, EN administered, body weight, AEs and concomitant medication.

During the first 28 days of treatment (initial treatment phase) physical examination findings, vital signs, body length, head circumference, conjugated bilirubin and results of biochemistry, hematology and coagulation analyses must be recorded weekly. If, at the end of the initial 28 days of treatment, PN is still indicated, patients may continue to receive the study drug until Day 84 (study extension phase).

On Day 29 the following criteria will be assessed: AEs, concomitant medications, physical examination findings, vital signs, body weight, body length, head circumference, conjugated bilirubin, results of biochemistry, hematology and coagulation analyses, α -tocopherol, sterols and fatty acids.

In the study extension phase physical examination findings, vital signs, body height, and head circumference must be recorded weekly. A blood sample for conjugated bilirubin, biochemistry, hematology and coagulation analyses will be collected every other week. However, should conjugated bilirubin exceed 1.5 mg/dL, it must be assessed weekly until conjugated bilirubin is again \leq 1.5 mg/dL. On Day 57 and Day 85, an additional blood sample will be collected for the determination of sterols, α -tocopherol and fatty acids.

Whenever a patient receives his/her last dose of study medication, an End-of-Treatment Visit will be performed the following day. The assessments for the End-of-Treatment Visit are the same as for the Day 29 Visit. If administration of IV lipids is required after the End-of-Treatment Visit, the standard lipid emulsion used in the daily routine at the respective participating site will be used.

A Follow-Up Visit must be performed 7 days after the End of Treatment Visit. At the Follow-Up Visit, all information regarding AEs and concomitant medications since the last study medication dose will be documented, and physical examination findings, vital signs, body

Clinical Study Protocol SMOF-018-CP3 Smoflipid 20% lipid injectable emulsion

weight, body length, and head circumference must be recorded. In addition, length-of-stay in the hospital will be recorded.

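### Discharge is observed only to about 8 days after the last dose in most infants, so the median time to discharge is likely overestimated or not reached

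*SAP*

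**What the plan says.** SAP 8.12.1.1 measures length of stay from randomization to discharge. On death it says "Death during hospitalization will be considered a competing risk", and on survivors without a discharge "Patients alive who are not reported to be discharged during the study will be censored at the last follow-up date". The planned output includes "the median time to discharge from hospital determined from the cumulative incidence function" and a Fine and Gray hazard ratio with a 95% confidence interval.

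The protocol sets the timing. Section 7.1: "Whenever a patient receives his/her last dose of study medication, an End-of-Treatment Visit will be performed the following day". Section 12.2.7: "The Follow-Up Visit will be performed 7 days after the End-of-Treatment Visit". Length of stay is entered at that follow-up visit (7.1: "In addition, length-of-stay in the hospital will be recorded"; the study schedule marks it there only). Section 13.3.5 ends the observation period at the last follow-up visit.

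The study outline and section 11.3 tie stopping of study drug to tolerated oral or enteral feeding. Section 12.2.5 limits study drug to Day 84 and extends follow-up for infants weaned with conjugated bilirubin above 1.5 mg/dL until it falls to 1.5 or below. The SAP does not define the last follow-up date for this endpoint, does not discuss dependent censoring and plans no sensitivity analysis for it.

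**The concern.** The Aalen estimator treats a censored infant as having the same outlook as those who remain under observation. Here the clock that censors an infant starts when study drug stops, and the usual reason for stopping is that the infant now tolerates enteral feeds. Infants who are weaned but still in hospital therefore leave the risk set after about 8 days. Infants still on PN stay in it and come to represent everyone.

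Length of stay is one of the evaluations added at the regulator's wish (protocol 5.2: "Per the request of the FDA, length of stay in hospital"). Now that confirmatory testing has been dropped, descriptive estimates are what readers will take from the trial. A median stay that is too long by days or weeks, or that cannot be read from the curve, would mislead them without any warning in the plan.

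**Working it through.** The plan gives no expected length of stay or censoring rate, so there is no figure of its own to reproduce.

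**1. How long discharge can be observed.** Last dose on day d; End-of-Treatment Visit on d + 1; Follow-up Visit on d + 1 + 7 = d + 8 (window ±1 day). With last dose on Day 84 the latest scheduled visit is Day 84 + 8 = Day 92.

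**2. Direction.** Suppose weaned infants go home at a constant daily rate 1/m, where m is the mean lag from weaning to discharge. On day t (before Day 84) let b be the number still on PN, a the number weaned but in hospital, and a8 the part of a weaned within the last 8 days.
- True discharge rate: (1/m) × a/(a + b)
- Rate seen under the rule: (1/m) × a8/(a8 + b)

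Since a8 ≤ a, the second rate cannot exceed the first. The curve rises too slowly and the median is late. If infants still on PN are also withdrawn and censored, b shrinks and the seen rate rises, which pulls the other way.

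**3. Inputs for the size.**
- PN duration: median 28 days, about 15% beyond 3 months (protocol 7.2). As a lognormal, with 3 months taken as 90 days: σ = ln(90/28)/z(0.85) = 1.168/1.036 = 1.127. It is counted from randomization, an assumption.
- Study drug stops at weaning or Day 84; censoring 8 days later (step 1).
- Weaning-to-discharge lag: not in the documents. **Assumption:** exponential, independent of PN duration, with m varied.
- 200,000 simulated infants per setting.

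**4. Results (days).**

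| Mean lag m | True median | Estimated median | Censored |
|---|---|---|---|
| 3 | 31 | 32 | 21% |
| 5 | 33 | 39 | 32% |
| 7 | 35 | 47 | 42% |
| 10 | 39 | 60 | 53% |
| 14 | 43 | 80 | 63% |
| 21 | 51 | not reached | 73% |

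A repeat run gave about 31 vs 33, 36 vs 48 and 44 vs 81 at lags of 3, 7 and 14 days, so the figures are good to about a day.

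**5. Hand check of the censored share.** Share weaned by Day 84: Φ(ln(84/28)/1.127) = Φ(0.975) = 0.835; each is censored if the lag exceeds 8 days, with probability e^(−8/m). Share on PN beyond Day 92: 1 − Φ(1.056) = 0.146, all censored. Those weaned between Day 84 and Day 92 (0.165 − 0.146 = 0.019) are partly censored. So the total lies between 0.835·e^(−8/m) + 0.146 and the same term + 0.165.
- m = 7: 0.835 × 0.319 = 0.266, giving 41% to 43% (simulated 42%).
- m = 14: 0.835 × 0.565 = 0.472, giving 62% to 64% (simulated 63%).

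**6. Sensitivity of the median (true vs estimated, days).**
- 5% deaths and 20% withdrawals at random: 35 vs 42 (m = 5), 38 vs 51 (m = 7), 46 vs 90 (m = 14).
- Withdrawals concentrated in infants with long PN, at 20% / 40%: 43 vs 74 / 63 (m = 14), 35 vs 44 / 40 (m = 7), 33 vs 37 / 35 (m = 5), 31 vs 31 / 30 (m = 3), 30 vs 29 / 28 (m = 2).
- Less variable lag (gamma, shape 3): 31 vs 31 (m = 3), 35 vs 49 (m = 7), not reached at m = 14.
- Narrower PN spread (log-SD 0.5 to 0.7, which puts only 1.0% to 4.8% beyond 90 days): 35–36 vs 38–41 (m = 7), 42 vs 50–59 (m = 14).
- Longer lags in earlier-weaned infants, two variants: 45 vs 60 and 41 vs 48 with the protocol 7.2 spread; 41 vs 43 and 38 vs 38 with log-SD 0.5.

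**7. With discharge dates collected** (365 days of follow-up after drug stop): 33 vs 33, 35 vs 35 and 43 vs 43 at m = 5, 7 and 14.

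**8. Treatment contrast.** With equal arms the hazard ratio stayed at about 1. With PN 20% shorter in one arm and no deaths, full follow-up versus the rule gave 1.42 vs 1.43, 1.34 vs 1.34 and 1.18 vs 1.19 (m = 7), and 1.39 vs 1.50, 1.28 vs 1.31 and 1.20 vs 1.22 (m = 14), for log-SD 0.5, 0.7 and 1.127. With median PN of 28 vs 24 days and m = 14, the true 4-day difference in median stay came out as 6 to 9 days.

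**The case against.** The endpoint is secondary and descriptive, with no tests or p-values. The SAP already tabulates the numbers discharged, dead and censored and lists patients, so heavy censoring would show. The SAP names the last follow-up date, not the Follow-up Visit. Infants with bilirubin above 1.5 mg/dL or unresolved adverse events are followed longer, and the length-of-stay worksheet, which might capture later discharges, is not in the available text. (The SAP cites it as Annex 6 to the protocol; the protocol calls it Annex 4.) The lag is assumed. Not everyone who stops study drug is near discharge: some stop for rising bilirubin, for other withdrawals or at Day 84.

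Much of this stands and limits the claim. A reader might infer that the median is certainly biased upward. The documents do not support certainty: they give no lag, and withdrawal of sicker infants, or longer lags after early weaning, can shrink or cancel the bias. A reader might also infer that every infant is censored 7 days after study drug ends. The visit is about 8 days after the last dose, and some infants are followed beyond it.

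What does not stand is that being descriptive makes the number harmless, or that a count of censored infants corrects a median printed beside it. Extended bilirubin follow-up is no remedy either: if it moves the last follow-up date, censoring then also depends on the liver outcome.

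**Conclusion.** The point holds for the median. Under the rule as written, censoring is tied to weaning, and the median from the cumulative incidence function is likely overestimated or not reached. With the PN distribution in protocol 7.2 and the simple exponential lag, the excess is about 2 days at a mean lag of 3 days (33 − 31), 12 at 7 days (48 − 36) and 37 at 14 days (81 − 44). At 21 days there is no median to report. These sizes rest on the assumed lag and on who is withdrawn.

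A reader might go further and infer that the hazard ratio is seriously biased because PN duration is what the trial compares. That is not supported. The primary comparison is confirmed conjugated bilirubin above 2 mg/dL, nothing in the documents shows that PN duration differs by arm, and the hazard ratio moved little in most settings. If PN duration does differ, the gap between the two arms' medians is more exposed than the hazard ratio. The point should be corrected before the results are reported, but it does not touch the primary endpoint.

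**What to change.** 1. Obtain the actual date of discharge or in-hospital death for each infant still hospitalised at the Follow-up Visit, and analyse time to discharge to that date.
2. Define the last follow-up date in SAP 8.12.1.1, including for infants followed longer for bilirubin, and correct the annex reference for the worksheet.
3. Where dates cannot be obtained, do not present the median from the cumulative incidence function as an estimate of length of stay. Report by arm the proportions discharged, still in hospital and dead at the Follow-up Visit, and state that censoring depends on weaning. The hazard ratio need not be dropped on this ground, but should carry the same statement.

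Cost: SAP version 2.0 (29 October 2020) follows early termination and the blinded review meeting of 28 October 2020, so step 1 means a query to up to 15 sites for one date per infant concerned. Step 3 needs only SAP wording. It gives a less informative summary, because the visit falls at a different time since randomization for each infant.
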